**10.10.9. Non ICH Listings**

Non-ICH : Listings					
No.	Population	IDSL / TST ID / Example Shell	Title	Programming Notes	Deliverable
Study Population: Subject Disposition					
15	ITT	IDSL_POP4	Listing of Subjects by Country and Centres		SAC
Study Population: Protocol Deviations					
16	ITT	IDSL_TA1	Listing of Treatment Sequence Misallocations		SAC
Study Population: Medical Conditions & Concomitant Medications					
17	ITT	IDSL_MH2	Listing of Medical Conditions		SAC
18	ITT	IDSL_SP05	Listing of Family History of Cardiovascular Risk Factors		SAC
19	ITT	IDSL_SP06	Listing of COPD History and COPD Exacerbation History		SAC
20	ITT	IDSL_SP07	Listing of Smoking History and Smoking Status		SAC
21	ITT	IDSL_CM2	Listing of COPD Medications		SAC
22	ITT	IDSL_CM2	Listing of Non-COPD Medications		SAC
23	ITT	IDSL_CM6	Relationship between ATC Level 1, Ingredient and Verbatim Text		SAC
Study Population: Devices					
24	ITT	IDSL_SP08	Listing of Naivety to Inhaler Devices		SAC
Efficacy: Secondary Efficacy Analysis					
25	ITT	EFF_L03	Listing of Preference Questionnaire		SAC
Safety					
26	ITT	IDSL_S3	Listing of COPD Exacerbations		SAC

Non-ICH : Listings					
No.	Population	IDSL / TST ID / Example Shell	Title	Programming Notes	Deliverable
27	ITT	IDSL_VS4	Listing of Myocardial infarction/unstable angina		SAC
28	ITT	IDSL_S06	Listing of Congestive heart failure		SAC
29	ITT	IDSL_VS4	Listing of Arrhythmias		SAC
30	ITT	IDSL_S06	Listing of Valvulopathy		SAC
31	ITT	IDSL_VS4	Listing of Pulmonary hypertension		SAC
32	ITT	IDSL_S06	Listing of Cerebrovascular events/stroke and transient ischemic attack		SAC
33	ITT	IDSL_S06	Listing of Peripheral arterial thromboembolism		SAC
34	ITT	IDSL_VS4	Listing of Deep venous thrombosis/pulmonary embolism		SAC
35	ITT	IDSL_S06	Listing of Revascularisation		SAC
36	ITT	IDSL_VS4	Listing of All cause deaths		SAC
37	ITT	IDSL_PREG1a	Listing of All subjects who became pregnant during the study		SAC

**10.11. Appendix 11: Example Mock Shells for Data Displays**

Example : EFF\_T01  
Protocol : 206901  
Population : Intent to Treat

Page 1 of 1

Table X.X  
Summary of errors on ELLIPTA

Inhaler errors test	After Reading Leaflet (Day 1) (N=XXX)	After 28 days use (N=XXX)	At early withdrawal visit (N=XXX)
Number of Subjects with Errors	XXX (XX%)	XXX (XX%)	XXX (XX%)
Number of Subjects with Critical Errors	XXX (XX%)	XXX (XX%)	XXX (XX%)
Total Number of Errors	XXX	XXX	XXX
Total Number of Critical Errors	XXX	XXX	XXX
Failed to open cover [1]	XXX (XX%)	XXX (XX%)	XXX (XX%)
Shook the device upside down after dose preparation [1]	XXX (XX%)	XXX (XX%)	XXX (XX%)
Inhalation manoeuvre: long, steady, deep	XXX (XX%)	XXX (XX%)	XXX (XX%)
Blocked air inlet during inhalation manoeuvre	XXX (XX%)	XXX (XX%)	XXX (XX%)
No exhalation before an inhalation	XXX (XX%)	XXX (XX%)	XXX (XX%)
Exhaled directly into mouthpiece [1]	XXX (XX%)	XXX (XX%)	XXX (XX%)
No seal by the lips round the mouthpiece during the inhalation [1]	XXX (XX%)	XXX (XX%)	XXX (XX%)
Did not hold breath	XXX (XX%)	XXX (XX%)	XXX (XX%)
Did not close the device	XXX (XX%)	XXX (XX%)	XXX (XX%)

[1] Indicates a Critical Error.

Note: Percentages for number of subjects are calculated from the total number of subjects who used the device(s), percentage of type of errors are calculated based on the number of subjects with errors.

Programming notes: Percentages for rows 1 and 2 are calculate from the total number of subjects in the ITT population shown in the heading, the remaining percentages are calculated based on the total number of subjects who had errors. For DISKUS + HandiHaler the first page should only contain the first four rows which will the overall summary of number of subjects with errors/critical errors and total number of errors/critical errors. The remaining two pages will be a replicate of the shell above but for two devices separately.

Example : EFF\_T02  
Protocol : 206901  
Population : Intent to Treat

Table X.X  
Summary and Analysis of Treatment Preference

	Total (N=XXX)	P-Value
-----		
Inhaler preference based on how easy it was to tell how many doses remain.		
n	XXX	X.XXX
ELLIPTA	XXX (XX%)	
DISKUS + HandiHaler	XXX (XX%)	
No Preference	XXX (XX%)	
Inhaler dosing regimen preference.		
n	XXX	X.XXX
ELLIPTA	XXX (XX%)	
DISKUS + HandiHaler	XXX (XX%)	
No Preference	XXX (XX%)	
Inhaler regimen preference based on the number of steps needed to take the medication.		
n	XXX	X.XXX
ELLIPTA	XXX (XX%)	
DISKUS + HandiHaler	XXX (XX%)	
No Preference	XXX (XX%)	

Note: The p-value is from the Cochran-Mantel-Haenszel Test.  
Programming notes: %'s calculated out of the small n for each question.

Example : EFF\_T04  
Protocol : 206901  
Population : Intent to Treat

Table X.X  
Analysis of Percentage of Participants making Zero Errors after 28 days use

	ELLIPTA (N=XXX)	DISKUS + HandiHaler (N=XXX)
Zero Errors	XXX (XX%)	XXX (XX%)
At Least one Error	XXX (XX%)	XXX (XX%)
ELLIPTA vs DISKUS + HandiHaler		
Odds Ratio	X.XX	
95% CI	(X.XX, X.XX)	
p-value	X.XXX	

Note: Odds ratio, 95% CI and p-value obtained from a conditional logistic regression model. Subject is included in the model as fixed strata, treatment option and period included as fixed effects.

Example : EFF\_T06  
Protocol : 206901  
Population : Intent to Treat

Table X.X  
Summary of Overall Errors

	Total (N=XXX)
Zero Errors on ELLIPTA	XXX (XX%)
At least one Error on ELLIPTA	XXX (XX%)
Zero Errors on DISKUS + HandiHaler	XXX (XX%)
At least one Error on DISKUS + HandiHaler	XXX (XX%)
Zero Errors on ELLIPTA or DISKUS + HandiHaler	XXX (XX%)
At least one Error on ELLIPTA and DISKUS + HandiHaler	XXX (XX%)
Number of subjects with discordant results [1]	XXX (XX%)
At least one Error on ELLIPTA and Zero Errors on DISKUS + HandiHaler [2]	XXX (XX%)
At least one Error on DISKUS + HandiHaler and Zero Errors on ELLIPTA [2]	XXX (XX%)

[1] Defined as an error in one device and not the other.

[2] Percentage is out of the number of subjects with discordant results.

Example : EFF\_T07  
Protocol : 206901  
Population : Intent to Treat

Table X.X  
Sensitivity Analysis of Percentage of Subjects making Zero Errors

	Result
-----	
Overall Errors	
Number of subjects with discordant results [1]	XXX
Number of subjects with an error on ELLIPTA	XXX (XX%)
Number of subjects with an error on DISKUS + HandiHaler	XXX (XX%)
p-Value [2]	
Critical Errors	
Number of subjects with discordant results [1]	XXX
Number of subjects with a critical error on ELLIPTA	XXX (XX%)
Number of subjects with a critical error on DISKUS + HandiHaler	XXX (XX%)
p-Value [2]	X.XXX

[1] Defined as an error in one device and not the other.

[2] Analysis performed using the Cochran-Mantel-Haenszel test

Note: Subjects are only included in the analysis if they have discordant data.

Example : EFF\_T08  
Protocol : 206901  
Population : Intent to Treat

Table X.XX  
Summary of Number and Change in Errors per Participant in Each Treatment Group

Treatment Group: ELLIPTA

Inhaler errors test		After Reading Leaflet (Day 1) (N=XXX)	After 28 days use (N=XXX)	Difference (Day 28 – Day 1) (N=XXX)
Overall Errors	n	XXX	XXX	XXX
	Minimum	XXX	XXX	XXX
	Medium	XXX	XXX	XXX
	Maximum	XXX	XXX	XXX
Critical Errors	n	XXX	XXX	XXX
	Minimum	XXX	XXX	XXX
	Medium	XXX	XXX	XXX
	Maximum	XXX	XXX	XXX

Note: n is the number of subjects making at least one overall/critical error

Programming notes: Page by ELLIPTA and DISKUS + HandiHaler.

Example : EFF\_T09  
Protocol : 206901  
Population : Intent to Treat

Table X.XX  
Tipping Point Analysis of Participants making Zero Errors after 28 days use  
(Supplementary Estimand: Composite)

Number of Subjects with Errors on DISKUS + HandiHaler (N=XX)	Number of Subjects with Errors on ELLIPTA (N=XX)				
	0	1	2	3	4
0	x.xx	x.xx	x.xx	x.xx	x.xx
1	x.xx	x.xx	x.xx	x.xx	x.xx
2	x.xx	x.xx	x.xx	x.xx	x.xx
3	x.xx	x.xx	x.xx	x.xx	x.xx
4	x.xx	x.xx	x.xx	x.xx	x.xx

Note: N is the total amount of missing data for each treatment option.  
Values in the table are p-values obtained from a conditional logistic regression model. Subject is included in the model as fixed strata, treatment option and period included as fixed effects.

Programming notes: If this doesn't fit into one table then use symbols to identify where  $p < 0.05$  or  $p \geq 0.05$  and add a footnote to explain.

Example : SAFE\_T01  
Protocol : 206901  
Population : Intent to Treat

Summary of On-Treatment COPD Exacerbations

	Overall (N=XXX) n (%)
Number of subjects an COPD exacerbation	XXX (XX%)
Total number of COPD exacerbations per subject	
n	XXX
0	XXX (XX%)
1	XXX (XX%)
2	XXX (XX%)
>=3	XXX (XX%)

[1] Percentages calculated using the total number of moderate/severe COPD exacerbations as the denominator.

[2] More than one treatment may be selected for a given exacerbation.

Note: Moderate exacerbations are defined as exacerbations that required treatment with systemic corticosteroids and/or antibiotics (not involving hospitalisation). Severe exacerbations are defined as exacerbations that required hospitalisation.

Example : SAFE\_T01  
Protocol : 206901  
Population : Intent to Treat

	Overall (N=XXX) n (%)
Total number of COPD exacerbations	XXX
Total number of exacerbations	XXX
Total number of exacerbations leading to withdrawal	XXX
Treatment [1][2]	
Took oral/systemic corticosteroids	XXX (XX%)
Took antibiotics	XXX (XX%)
Visited emergency room	XXX (XX%)
Hospitalised	XXX (XX%)
Intubated	XXX (XX%)
Outcome [1]	
Resolved	XXX (XX%)
Fatal	XXX (XX%)
Not resolved	XXX (XX%)

[1] Percentages calculated using the total number of COPD exacerbations as the denominator.

[2] More than one treatment may be selected for a given exacerbation.

Note: Moderate exacerbations are defined as exacerbations that required treatment with systemic corticosteroids and/or antibiotics (not involving hospitalisation). Severe exacerbations are defined as exacerbations that required hospitalisation.

Example : SAFE\_T01  
Protocol : 206901  
Population : Intent to Treat

	Overall (N=xxx)
Duration of moderate/severe COPD exacerbation (days)	
n	xxx
Mean	xx.x
SD	xx.xx
Median	x.x
Min.	xx
Max.	xx

[figure not shown]
[1] Percentages calculated using the total number of moderate/severe COPD exacerbations as the denominator.

[2] More than one treatment may be selected for a given exacerbation.

Note: Moderate exacerbations are defined as exacerbations that required treatment with systemic corticosteroids and/or antibiotics (not involving hospitalisation). Severe exacerbations are defined as exacerbations that required hospitalisation.

Example : EFF\_F01  
Protocol : 206901  
Population : Intent to Treat

Figure X.X  
Percentage of Participants with Zero Errors and Zero Critical Errors by Treatment Group

Example : EFF\_L01  
Protocol : 206901  
Population : Intent to Treat

Listing X.X  
Listing of Subject Errors by Assessment

Sub-study 1: ELLIPTA vs DISKUS + HandiHaler

Subject ID	Period	Treatment	Assessment	Total Errors	Device	Type of Error
XXXX	1	ELLIPTA	After reading the PIL	2	ELLIPTA	Exhaled directly into mouthpiece Failed to open cover
			After 28 days use	1	ELLIPTA	Did not hold breath
	2	DISKUS + HandiHaler	Reading the PIL	3	DISKUS	Failed to open cover Lever is not pushed back
			After 28 days use	2	HandiHaler DISKUS HandiHaler	Did not hold breath Failed to open cover Did not hold breath [1]

...

[1] Indicates a Critical Error.

Example : EFF\_L02  
Protocol : 206901  
Population : Intent to Treat

Listing X.X  
Listing of Preference Questionnaire

Sub-study 1: ELLIPTA vs DISKUS + HandiHaler

Subject ID	Treatment Sequence	Question 1	Question 2	Question 3
XXXX	ELLITA/DISKUS + HandiHaler/Q1	ELLIPTA	ELLIPTA	ELLIPTA
XXXX	DISKUS + HandiHaler/ELLIPTA/Q2	DISKUS + HandiHaler	DISKUS + HandiHaler	ELLIPTA
XXXX	ELLITA/DISKUS + HandiHaler/Q2	No Preference	No Preference	No Preference

...

Note: Q1 = Questionnaire 1, Q2 = Questionnaire 2  
Question 1 = Inhaler preference based on how easy it was to tell how many doses remain.  
Question 2 = Inhaler dosing regimen preference  
Question 3 = Inhaler regimen preference based on the number of steps needed to take the medication

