10.2. Sample Size Determination

The sample size calculations for this study have been based on the primary endpoint, which is the percentage of participants making zero errors in each treatment group (ELLIPTA or DISKUS + HandiHaler) after 28 days use.

The estimates of inhaler errors were taken from the overall errors reported in the 200301 study for each individual inhaler (ELLIPTA, DISKUS and HandiHaler) separately. Although this study is only assessing combined errors in the DISKUS + HandiHaler treatment group, individual inhaler errors were used to estimate the combined error rate in order to provide a conservative estimate. By doing this it assumes that participants, who made no errors on the DISKUS inhaler, would not make any errors of the HandiHaler inhaler and vice-versa.

As the 200301 study only had a single visit, no estimates were available for error rates over 28 days, however the study did provided estimates of participant errors after reading the PIL and after being instructed on correct use by a HCP up to three times. As participants will have the PIL for 28 days, and can be instructed by a HCP at the inhaler dispensing visit if necessary, both estimates of error rates along with a sensitivity analysis examining some of the potential error rates between were used to inform sample size calculations.

Using 10,000 simulations, a total of 216 participant (54 per treatment sequence) provide at least 90% power to show a statistically significance difference between the overall error rate of the ELLIPTA inhaler versus DISKUS + HandiHaler inhalers, for all of the paired treatment error rates shown in [Table 1](#).

Table 1 Error rates of ELLIPTA vs. DISKUS + HandiHaler achievable with 90% power, 5 % Type 1 error using a total of 216 participants

ELLIPTA Error Rate	DISKUS + HandiHaler Error Rate
33%	>=50%
30%	>=47%
20%	>=35%
10%	>=23%
5%	>=15%

Conditional logistic regression and a two-sided 5% significance level were used as the analysis method for all simulations performed. As it is expected that some participants would drop out or change inhalers during the study, with 10% withdrawal it would be

necessary to enrol 240 participants (60 per treatment sequence) to ensure there were 216 participants with evaluable data at the end of the study.

For the purpose of this study an evaluable participant is defined as a randomized participant who completed error assessments for both randomized treatment groups.

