## **7.2. Secondary Efficacy Analyses**

### **7.2.1. Endpoint**

- 1) Percentage of participants with zero critical errors after 28 days of use.
- 2) Number of errors by type for each inhaler after 28 days use
- 3) Number and change in errors per participant for each treatment group (V2 and V3) after 28 days use
- 4) Number and change in errors for each treatment group in participant with one or more errors after 28 days use

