**10.10.5. Efficacy Tables**

Overall Summary of Errors					
No.	Population	IDSL / TST ID / Example Shell	Title	Programming Notes	Deliverable
2.01	ITT	EFF_T01	Summary of Errors on ELLIPTA		SAC
2.02	ITT	EFF_T01	Summary of Errors on DISKUS + HandiHaler	Page by DISKUS + HandiHaler Errors, DISKUS Errors and HandiHaler Errors	SAC
2.03	ITT	EFF_T06	Summary of Overall Errors		SAC
2.04	ITT	EFF_T06	Summary of Overall Errors by Age	Use age categories: 40-64, 65-74 and $\geq 75$ .	SAC
2.05	ITT	EFF_T06	Summary of Critical Errors		SAC
Primary Efficacy Tables					
Percentage of Overall Errors					
2.06	ITT	EFF_T04	Analysis of Percentage of Participants making Zero Errors after 28 days use (Primary Estimand: Principle Strata)		SAC
2.07	ITT	EFF_T04	Analysis of Percentage of Participants making Zero Errors after 28 days use (Supplementary Estimand: Composite)		SAC
2.08	ITT	EFF_T09	Tipping Point Analysis of Participants making Zero Errors after 28 days use (Supplementary Estimand: Composite)		SAC
2.09	ITT	EFF_T07	Sensitivity Analysis of Percentage of Participants making Zero Errors after 28 days use (Primary Estimand: Principle Strata)		SAC

Overall Summary of Errors					
No.	Population	IDSL / TST ID / Example Shell	Title	Programming Notes	Deliverable
2.10	ITT	EFF_T07	Sensitivity Analysis of Percentage of Participants making Zero Errors after 28 days use (Supplementary Estimand: Composite)		SAC
Secondary Efficacy Tables					
Percentage of Critical Errors					
2.11	ITT	EFF_T04	Analysis of Percentage of Participants making Zero Critical Errors after 28 days use (Primary Estimand: Principle Strata)		SAC
Number of Overall Errors					
2.12	ITT	EFF_T01	Summary of Number of Errors by Type for each Inhaler after 28 Days of Use	Replace 'Early withdrawal' column with 'Difference (ELLIPTA minus DISKUS + HandiHaler)	SAC
2.13	ITT	EFF_T08	Summary of Number and Change in Errors per Participant for each Treatment Group (V2 and V3) after 28 Days of Use		SAC
2.14	ITT	EFF_T08	Summary of Number and Change in Errors for each Treatment Group in Participants with One or more Errors after 28 Days of Use		SAC
Exploratory Efficacy Tables					
Preference Attributes					
2.15	ITT	EFF_T04	Analysis of Percentage of Participants with Zero Errors after 28 Days of Use, including the Number of Prescribed Maintenance Inhalers as a Covariate.		SAC

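### Shell EFF_T08 defines n as participants with at least one error, but it also serves Table 2.13, whose endpoint has no such restriction; the footnote needs correcting on either reading

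*SAP*

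**What the plan says.** SAP 7.2.1 lists two endpoints that differ only in who is counted. Endpoint 3 is "Number and change in errors per participant for each treatment group (V2 and V3) after 28 days use". Endpoint 4 is "Number and change in errors for each treatment group in participant with one or more errors after 28 days use". Protocol section 4 makes the same distinction. SAP 7.2.3 sets the Intent-to-Treat population for both, and SAP 7.2.5 and Protocol 10.4.1 say that both are summarised without a test.

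SAP 10.10.5 gives each endpoint a table. Table 2.13 is titled "Summary of Number and Change in Errors per Participant for each Treatment Group (V2 and V3) after 28 Days of Use" and Table 2.14 "Summary of Number and Change in Errors for each Treatment Group in Participants with One or more Errors after 28 Days of Use". Both name shell EFF_T08, and the programming-notes cell is blank for each.

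In SAP Appendix 11, EFF_T08 carries the per-participant title. Its columns are the assessment after the leaflet, the assessment after 28 days, and the difference, each with its own heading N. It has one block for overall errors and one for critical errors. Each block prints n, then minimum, median (spelled Medium) and maximum. The footnote is "Note: n is the number of subjects making at least one overall/critical error". The shell's own programming note deals only with paging by device.

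**The concern.** One shell cannot serve both tables with one definition of n. The footnote describes, roughly, the subset for endpoint 4. Carried into Table 2.13, it would place endpoint 4's restriction on endpoint 3, and the overall-error Day 28 column of Table 2.13 would repeat that of Table 2.14.

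At stake is the distribution of the per-participant number of errors, and of its change, with error-free participants counted as zeros. The SAP plans no other table of that distribution. SAP 2.1 also declares no departure from the protocol's planned analysis, so restricting endpoint 3 through a footnote would be an undeclared one.

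**Working it through.** **Inputs.** Protocol 10.2: 216 evaluable participants, 10% withdrawal, 240 enrolled, and Table 1, titled "Error rates of ELLIPTA vs. DISKUS + HandiHaler achievable with 90% power, 5 % Type 1 error using a total of 216 participants". The ELLIPTA error rates are 33, 30, 20, 10 and 5%. The paired DISKUS + HandiHaler rates are lower bounds: 50, 47, 35, 23 and 15%. The number assessed at Day 28 is taken as 216, which is an assumption.

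**The plan's own figures.** 216 / (1 − 0.10) = 240, as stated. Simulating the five pairs (10,000 runs each, 108 per device sequence, conditional logistic regression with treatment and period, within-participant correlation assumed to be 0) gave power of 94.9, 95.2, 93.9, 95.6 and 93.4%, consistent with the stated minimum of 90%. The point here does not alter these figures.

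**Step 1: what n means elsewhere in Appendix 11.** In EFF_T02, percentages for each preference question are taken out of n. In SAFE_T01, the block headed "Total number of COPD exacerbations per subject" has an n row followed by a category for 0, so n there includes people with no event. SAFE_T01's duration block places n above mean, SD, median, minimum and maximum. In each case n is the number summarised.

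**Step 2: size on that reading.** n at Day 28 is 216 × p, and the number left out is 216 × (1 − p), where p is the error rate.

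| ELLIPTA rate | n | Left out | DISKUS + HandiHaler rate (lower bound) | n (at least) | Left out (at most) |
|---|---|---|---|---|---|
| 33% | 71 | 145 | 50% | 108 | 108 |
| 30% | 65 | 151 | 47% | 102 | 114 |
| 20% | 43 | 173 | 35% | 76 | 140 |
| 10% | 22 | 194 | 23% | 50 | 166 |
| 5% | 11 | 205 | 15% | 32 | 184 |

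The critical-error block would lose at least as many, because every critical error is also an error.

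**Step 3: effect on the printed statistics.** Among people with at least one error, the minimum and the median are each at least 1. Over everyone assessed, the minimum is 0 if anyone is error-free, and the median is 0 if fewer than half err. At exactly half, the median over everyone lies between 0 and the smallest positive count: 108 zeros and 108 ones give 0.5. In the number columns the maximum does not change as long as someone errs.

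**Step 4: the other reading.** Suppose that n only counts people with an error, while minimum, median and maximum use everyone assessed. Table 2.13 then has the right statistics under a misleading n. But the same shell, used for Table 2.14, no longer restricts anything unless the programmer takes the restriction from the table title. So no single reading of the footnote makes both tables right.

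**Step 5: fit to Table 2.14.** Endpoint 4 restricts to participants with one or more errors. In the critical-error block, the footnote's n would be those with a critical error, which is a smaller set. Nor does the footnote tie the subset to Day 28 in the leaflet and difference columns. It is therefore only an approximate fit even there.

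**The case against.** The strongest reply is that the footnote defines one row label and nothing more. It does not say that minimum, median and maximum use the same subset. The population is ITT, the heading N is printed separately, and the shell's title is per participant. The special note might exist precisely because n differs here from the other shells. The SAP also refers continuous summaries to an internal standard that is not reproduced. This stands: exclusion is the natural reading, not the only one. It does not rescue the footnote, because the alternative leaves n mislabelled and Table 2.14 without its restriction.

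A reader might infer that endpoint 3 goes unreported. The documents do not support that. Table 2.13 is listed and titled for it. Zero-error counts appear in the tables on EFF_T04 and EFF_T06. Tables 2.01 and 2.02 print total errors and numbers with errors at both time points, so a mean per participant can be worked out. Listing 14 gives individual counts.

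A reader might also infer that the difference column omits a known number of people who went from errors to none. The shell does not say which column's subset governs the difference. Table 1 lists pairs of rates for power, not a course from dispensing to Day 28. The direction of such a selection is clear; its size cannot be taken from the documents.

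Finally, a reader might see a contradiction in EFF_T01, where the footnote bases the first two rows on users of the device and the programming note on the ITT number in the heading. That shell prints an N for every column, including early withdrawal, so the two most plausibly agree. Only the wording needs tidying.

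**Conclusion.** The point holds as a defect in the shell specification. A single definition of n serves two endpoints that need different sets. On the ordinary reading, Table 2.13 would leave out 145 to 205 of 216 participants on ELLIPTA, and at most 108 to 184 on DISKUS + HandiHaler, at Day 28. These counts rest on three things: that n is the number summarised, that 216 are assessed, and that the error rates are those in Table 1. The second group's counts are maxima because its rates are lower bounds.

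The reach is limited. Both endpoints are descriptive, and the primary and critical-error analyses, sample size and power do not change. What lacks a correct table is the distribution of the per-participant number and change with zeros included. The change is worth making before programming, because it affects a prespecified secondary endpoint and costs little.

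**What to change.** - **Table 2.13:** define n as all participants with a non-missing assessment on that device at that time point (both time points for the difference), zeros included. Compute every statistic on that set.
- **Table 2.14:** add a separate note restricting to participants with one or more errors of any type at Day 28. Use that one set in every column and in both the overall-error and critical-error rows. Keep its change column.
- **Both tables:** SAP 10.7.2.2 sets an assessment to an error when only one of the two devices was completed and an error was made on it. The error count is then incomplete, so the notes should say whether it enters.
- **EFF_T01 (wording only):** state that the heading N is the number assessed on that device at that time point, so that footnote and programming note agree.

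The cost is edits to shell footnotes and programming notes. No new data are needed, and endpoints 3 and 4 stay as worded.
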